- Eligibility Source documents: Initial consult note, pre-implant sleep study, pre-implant DISE report, HGNS titration report, HGNS efficacy sleep study report (if applicable), current medications list (reconciled), all Inspire® therapy reports leading up to enrollment.

4C. Study Timeline - Pages 5 to 10

- Enrollment (Study Day 1): HGNS therapy will be deactivated (set to 0.0 V) for one week. Sham threshold determination may be done during this visit, or during randomization visit (see below study week 2). RSC will schedule cardiovascular and sympathetic testing, if possible. The patient will also be instructed about neurobehavioral testing and will perform a practice administration of the DSST and PVT. Form 1 will be completed by RSC (remote #, current therapy status, non-dominant arm diameter, WatchPAT digit determination, medication reconciliation, sham threshold determination (volts), and active therapy setting (volts)). If needed, the patient will contact RSC after the appointment to provide the remote number. The patient will also be given an "on-study card" containing contact information for the research coordinator. The patient will be told to contact the coordinator if any health care providers intend to make changes to the patient's blood pressure medication. An enrollment questionnaire will be completed by the patient:
 - o Do you take any medications or substances to improve daytime alertness?
 - Do you take any medications or substances to improve sleep quality?
 - o How many hours do you sleep each night, on average?
 - ESS, ISI, FOSQ, Snoring VAS
- Washout Period 1 (Study Week 1): The patient will not use HGNS for 1 week
- Randomization Visit (Study Week 2 with [name] and RSC):
 - a. Patient will fill out "washout questionnaire":
 - Patient attestation statement about therapy non-use
 - Have you taken any substance to increase daytime alertness (e.g. caffeine)?
 - Have you taken any substance to improve sleep quality (e.g. alcohol)?
 - o Have you had any episodes of falling asleep while driving?

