- b. Sham Threshold Determination (Consent or Randomization Visit): Mouth open, nose breathe only, stimulation from 0.1V up by 0.1-0.2V at same electrode configuration as at last clinic visit, level at which bulk tongue motion detected without obvious protrusion. This process is repeated and the average value is used to determine "sham-HGNS". This threshold will be used to define "sub-therapeutic amplitude" (sham). The electrode configuration will remain consistent between the patient's therapeutic and sham thresholds.
- c. Randomization: The research coordinator will program the device at the specified amplitude level: either "sham-HGNS" as above, or "therapeutic HGNS," depending on which is assigned first (**see part d below**). The "therapeutic HGNS" setting will be the patient's incoming amplitude on enrollment day which will have been predetermined as part of routine clinical care prior to enrollment in the study. The patient control range will be deactivated for consistency, i.e. there will only be one allowable setting. The research coordinator will instruct the patient to use therapy the same night, and for every night until the next washout after cardiovascular test day (study week 6).
- d. Randomization technique: Both patients and investigators will remain blinded regarding patient intervention (sham or treatment HGNS). Only the research coordinator will remain unblinded; he will randomize the patients using a simple scheme (sealedenvelope.com) and will not take part in any assessments. Block design (block size = 10 with 10 units per block) for total of 100 potential subjects. Number 1 = Sham First, Number 2 = Treatment First.
- Blinding Adequacy Phone Call (Week 2, Day 2)

A blinded member of the study team, as delegated by the PI, will contact the patient and perform a verbal questionnaire:

- 1. Do you think you are on "low" or "regular" treatment, or do you not know?
- 2. Why you do think so?
 - a. Increased snoring per bed partner
 - b. Increased fatigue
 - c. Morning headache
 - d. Nighttime awakening
 - e. Other
- Weekly Check-In Phone Call (Week 3, Week 4, Week 5)

RSC weekly call with patient re: usage. Goal is to encourage use (>20h/week) RSC will document changes in blood pressure medication, if applicable. RSC will remind the patient to consistently take the blood pressure medication. Any questions, comments, concerns, or AEs will be documented at this time as well.

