- Sympathetic Measurements (Study Week 6, Day 2): The patient will be laid supine in a comfortable position prior to testing. The 15-minute protocol will involve pre-ejection period (PEP) testing by impedance cardiography.

Prior to the testing, subjects will have been informed of the pre-visit protocol: no food >6 hours before testing; withhold all cardiac and blood pressure medications on the day of testing; no caffeine or alcohol >12 hours before testing; avoid exercise on morning of testing; refrain from cigarette smoke exposure >12 hours before testing; and abstain from vitamin supplementation >72 hours before testing.

Pre-ejection Period (PEP): Each patient will be fitted with the Biopac NICO100C Impedance Cardiography (ICG) Noninvasive Cardiac Output Module (Biopac, Goleta CA USA). This device will record the ECG and the ICG continuously during a 10-minute period through eight, disposable, pre-gelled Ag/AgCl electrodes. PEP will be calculated as the average interval (milliseconds) from the onset of left ventricular depolarization, reflected by the Q-wave onset in the ECG to the opening of the aortic valve, reflected by the B-point in the ICG signal.

- o At the end of this visit, the patient will be set to 0.0V for washout period 2.
- Procedure Day Questionnaire: Therapy attestation statement, medication reconciliation, caffeinated beverages per day, sleep-promoting substance use (e.g. alcohol), ESS, FOSQ, ISI, Snoring VAS.
- Neurobehavioral Measurements (Study Week 6, Day 2): The patient will perform neurobehavioral tests on a designated laptop in a quiet room at the Otorhinolaryngology clinic. Each subject will perform a unique version of the digital symbol substitution test

and psychomotor vigilance test. The laptop is calibrated for timing precision. All patients will be monitored by a trained study staff member to ensure adherence to test procedure protocol.

Prior to testing, subjects will have been informed of pre-visit protocol: abstain from testing if sick; abstain from testing if <1 hour of waking up; and abstain from testing if >16 hours of being awake.

- Washout Period 2 (Study Week 6-7): The patient will not use HGNS for 7 days.

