- Crossover Visit & Therapy (Study Week 7): The patient will be switched to the other intervention arm (treatment to sham vs. sham to treatment) for 28 days, or for the duration spent on the previous intervention arm. The research coordinator will program the device at the specified amplitude level, per Form 1.

Patient will fill out "washout questionnaire #2":

- Patient attestation statement about therapy non-use.
- Have you taken any substance to increase daytime alertness (e.g. caffeine)?
- Have you taken any substance to improve sleep quality (e.g. alcohol)?
- o Have you had any episodes of falling asleep while driving?

The research coordinator will reprogram the patient's HGNS to the amplitude the patient was using prior to study participation. The research coordinator will instruct the patient to use therapy the same night.

• Blinding Adequacy Phone Call (Week 7, Day 2)

Phone call: second morning questionnaire:

- 1. Do you think you are on "low" or "regular" treatment?
- 2. Why you do think so?
 - a. Increased snoring per bed partner
 - b. Increased fatigue
 - c. Morning headache
 - d. Nighttime awakening

e.	Other					

Weekly Check-In Phone Call (Week 8, Week 9, Week 10)

RSC weekly call with patient re: usage. Goal is to encourage use (>20h/week). Document any changes in blood pressure medication.

Document any AEs, issues or concerns.

• 24-hour Ambulatory Blood Pressure & WatchPAT (Study Week 9, Night 1):

The patient will be programmed and mailed 24-hour ambulatory blood pressure testing (ABP) and WatchPAT, scheduled to arrive between 2-7 days before physiology testing.

RSC will ensure that ABP, WatchPAT and Inspire® times are synchronized. For convenience and/or patient preference, the patient may meet with RSC in person to pick up the equipment.

- Sympathetic, Vascular, & Neurobehavioral Measurements & Wrap-Up (Study Week 10, Day 2):
 - 1. RSC will download therapy compliance data from the patient's remote.
 - 2. The patient will undergo the same set of testing as above.
 - 3. If any of the ABP or WatchPAT data is invalid or incomplete, the patient may be asked to repeat these tests, at the discretion of the PI. In this case, the patient will remain at the current setting and will need to return to have their HGNS reset to the pre-study amplitude.
 - 4. Procedure Day Questionnaire: Therapy attestation statement, medication reconciliation, caffeinated beverages per day, sleep-promoting substance use, ESS, FOSQ, ISI, Snoring VAS.

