 - 5. Exit Questionnaire
 - 6. The patient will resume usual care: the RSC will reprogram the patient's HGNS to the pre-study therapeutic amplitude and will reactivate the stimulation control range. The patient will be encouraged to contact the study team to address any problems or questions.

5. Variables:

Medical Chart: age, sex, race, smoking status, hypertension status, diabetes status, apnea-hypopnea index (AHI) from pre-operative sleep study, ODI from pre-operative study, pre-operative DISE report, history of PAP intolerance

Study Data (Clinical): body-mass index, current medications (recorded each study visit), therapy usage (hours/week)

Study Data (Experimental): mean systolic and diastolic blood pressures over 24 hours, mean systolic and diastolic blood pressures during sleep, WatchPAT ODI and AHI from both sham and active therapy tests, pre-ejection period (milliseconds), flow-mediated dilation, peripheral arterial stiffness (PWV in m/s, AIX, SEVR), Snoring Visual Analog Scale (VAS), Epworth Sleepiness Scale (ESS), Insomnia Severity Index (ISI), Functional Outcomes Sleep Questionnaire (FOSQ-10)

6. Analysis

The overall analysis plan is to examine changes in all cardiovascular endpoints over time (i.e., sham to treatment or treatment to sham) as well as internal correlation of these endpoints. Sex, a relevant biological variable, is a covariate in all analyses.

For **Aim 1**, we will perform a paired t-test to compare sham and active therapy 24-hour systolic ambulatory blood pressure values. Improvement in AHI will be calculated as the

difference between pre-operative and post-operative AHI. Multivariable linear regression models will be used to estimate associations between blood pressure reduction (outcome variable) and improvement in AHI (main effect variable) Final models will include age, sex, body-mass index, baseline systolic BP, baseline diastolic BP, antihypertensive medication use.

- H1: Therapeutic levels of HGNS will reduce mean 24-hour systolic pressures
- **H2:** Therapeutic levels of HGNS will further reduce mean sleep systolic and diastolic pressures

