For Hypotheses 1 & 2, for the purposes of sample size estimation, we are using t-test (bivariate) calculation rather than multivariate analysis. Historical data from an OSA cohort demonstrated an overall 24-hour mean systolic pressure of 133mmHg, with a standard deviation=11. 40 We estimate a clinically significant difference in systolic blood pressure to be 4mmHg⁴¹ which, at the population level, reduces mortality from stroke by 10-40% and mortality from ischemic heart disease or other vascular causes by 7-10%. 42 With significance level α = 0.05 (two-tailed) and power 1- β = 0.80, to test a difference in blood pressure of 4mmHg between two repeated measures, a sample of **n=60** would be needed.

For **Aim 3**, we will perform paired t-tests to compare sham and therapy values for both MSNA bursts/minute and pre-ejection period duration. Note that MSNA will no longer be performed at the University of Pennsylvania.

H1: Therapeutic levels of HGNS will reduce muscle sympathetic nerve activity, a direct measure of sympathetic activity

**H2**: Therapeutic levels of HGNS will increase the duration of the pre-ejection period, an indirect measure of sympathetic activity

For the purposes of sample size estimation for H1, in a published study of OSA patients measuring baseline MSNA, mean MSNA was 39 bursts/min (s.d. = 4). ³³ While MSNA is not a commonly used clinical outcome measure, we estimate a significant difference in MSNA to be 5 bursts/min, based on documented effect of CPAP therapy on MSNA. ¹⁴ With significance level α = 0.05 (two-tailed) and power 1- β = 0.80, to test a difference in MSNA of 5 bursts/min between two repeated measures, a sample of **n=11** would be needed.

For Hypothesis 2, published PEP values in a cohort of OSA patients had a mean of 93 milliseconds (s.d.=17.3). ³⁶ Based on comparative data between untreated apneics and non-apneics, we estimate a significant difference in PEP to be a 10 millisecond increase from baseline. ³⁶ With significance level α = 0.05 (two-tailed), power 1- β = 0.80, to test a difference in PEP of 10 milliseconds, a sample of **n=47** would be needed.

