For **Aim 4**, we will perform linear regression with MSNA bursts/min and PEP duration as outcome variable and systolic and diastolic blood pressures as main effect variables. We will determine if MSNA and PEP are positively associated with blood pressure measurements while adjusting for confounders of age, sex, body-mass index, baseline systolic BP, baseline diastolic BP, antihypertensive medication use.

H1: There will be a significant association between alterations in systolic and diastolic

blood pressure and muscle sympathetic nerve activity

**H2**: There will be a significant association between alterations in systolic and diastolic blood pressure and pre-ejection period duration

With n=45, we would exceed 95% power to detect effects in the moderate to large range ($r^2 > 0.25$) assuming a two-tailed $\alpha = 0.05$. With smaller effects ($r^2 > 0.16$) power drops somewhat (78%) but still affords a reasonable opportunity to reject the null hypothesis of an association among these various measures of sympathetic function.

For **Aim 5**, we will perform a paired t-test to compare sham and active therapy DSST scores. Improvement in DSST score will be calculated as the difference between the score at therapeutic levels and the score after 30-day sham period. Multivariable linear regression models will be used to estimate associations between DSST score (outcome variable) and improvement in AHI (main effect variable). Final models will include age, sex, body-mass index, baseline DSST.

H1: DSST score will increase during therapeutic levels of HGNS compared to after the 30- day sham period.

For **Aim 6**, we will perform a paired t-test to compare sham and active therapy PVT reaction time scores. Improvement in PVT reaction time score will be calculated as the difference between the score at therapeutic levels and the score after 30-day sham period. Multivariable linear regression models will be used to estimate associations between PVT score (outcome variable) and improvement in AHI (main effect variable). Final models will include age, sex, body-mass index, baseline PVT.

H1: PVT reaction time score will decrease during therapeutic levels of HGNS compared to after the 30-day sham period.

7. Risk / Benefit

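### The randomised two-period crossover is compared by paired t-tests with no period term (Aims 1, 3, 5 and 6); adjusting for period costs about one degree of freedom

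*Combined protocol and SAP*

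**What the plan says.** Section 4C sets up a randomised two-sequence, two-period crossover. The randomisation item assigns sham first or treatment first: "Block design (block size = 10 with 10 units per block) for total of 100 potential subjects". After the second washout, the crossover item says "The patient will be switched to the other intervention arm (treatment to sham vs. sham to treatment) for 28 days" (or for as long as the first period lasted).

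Section 6 then compares the two conditions without using the assigned order:

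- Aim 1 (primary): "we will perform a paired t-test to compare sham and active therapy 24-hour systolic ambulatory blood pressure values".
- Aim 3: "we will perform paired t-tests to compare sham and therapy values for both MSNA bursts/minute and pre-ejection period duration" (the plan notes that MSNA is no longer done at the University of Pennsylvania).
- Aim 5: "we will perform a paired t-test to compare sham and active therapy DSST scores".
- Aim 6: "we will perform a paired t-test to compare sham and active therapy PVT reaction time scores".

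The regressions in Aims 1, 5 and 6 relate the outcome to improvement in AHI, with patient characteristics and baseline values as covariates. They are not treatment comparisons and carry no period or sequence term. The opening of Section 6 mentions both orders of change but models neither.

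**The concern.** In a crossover, anything that moves all patients between the first and second measurement (season, visit familiarity, drift in medication, practice) enters the active-minus-sham difference with opposite signs in the two sequences. A paired t-test pools the sequences, so it counts that systematic shift as random error. If the sequences are equal in size, the shift cancels from the estimate but inflates its standard error. If they complete in unequal numbers, part of the shift stays in the estimate as bias.

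At stake are some power in a trial whose own Section 10 (Study Results, item b) warns of a type II error, and protection against a small bias if dropout differs by sequence. For DSST and PVT the plan reduces practice effects: at enrollment the patient "will perform a practice administration of the DSST and PVT", and later "Each subject will perform a unique version of the digital symbol substitution test" and of the PVT. Any practice effect that remains is still not modelled.

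**Working it through.** **Inputs.** From Section 6: SD 11 mmHg, difference 4 mmHg, two-sided alpha 0.05, power 0.80, n=60. From Section 10 (Study Results, item b): power 0.56 for 3 mmHg at n=60. Assumed: 1:1 allocation within blocks (the ratio is not stated), hence 30:30, and a period shift of 0 to 5.5 mmHg (the documents give none).

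**1. The plan's own figures.** Paired normal approximation: n = ((1.95996 + 0.84162) × 11/4)² = 59.36, rounded up to 60. Power for 3 mmHg: Φ(3/(11/√60) − 1.96) = 0.561, against the stated 0.56. Both reproduce, so 11 is being used as the SD of the paired difference. With the t distribution (59 df), power for 4 mmHg at n=60 is 0.791.

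**2. Effect of a shift.** Let τ be the active-minus-sham effect and π the period-2-minus-period-1 shift. The expected difference is τ + π in sham-first patients and τ − π in treatment-first patients. Hence:

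- mean of the paired differences = τ + π(n_sham-first − n_treatment-first)/N;
- at 30:30 the bias is zero, but the estimated variance rises to about 11² + π².

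**3. Paired t-test at 30:30, true effect 4 mmHg.** The mean difference is N(4, 121/60). Independently, 59·S²/121 is noncentral chi-square with 59 df and noncentrality 60π²/121. Integrating the rejection probability numerically (effect set to 0 for type I error) gives:

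| Assumed shift (mmHg) | Power | True type I error |
|---|---|---|
| 0 | 0.791 | 0.050 |
| 1 | 0.789 | 0.049 |
| 2 | 0.782 | 0.046 |
| 3 | 0.769 | 0.042 |
| 4 | 0.752 | 0.037 |
| 5.5 | 0.717 | 0.029 |

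**4. Period-adjusted comparison at 30:30.** The estimate is the average of the two sequence-specific mean differences. SE = (11/2)·√(1/30 + 1/30) = 1.420, the same as 11/√60. The df fall from 59 to 58 and the critical t rises from 2.0010 to 2.0017. Power is 0.7910 at every shift, against 0.7912 for the paired test when there is no shift.

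**5. Unequal completion, illustrated by 30:24.** Bias of the paired estimate = π × 6/54 = 0.111π: 0.22 mmHg at a 2 mmHg shift and 0.44 mmHg at 4 mmHg. Its direction depends on which sequence is short. The adjusted estimate is unbiased, with SE = (11/2)·√(1/30 + 1/24) = 1.506, 52 df and power 0.741. With no shift, the paired test has SE 11/√54 = 1.497, 53 df and power 0.747.

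**6. Other values of the SD.** Section 6 quotes 11 as a cohort SD. Using it as the SD of the difference implies a within-patient correlation of 0.5, since SD_diff = 11·√(2(1 − ρ)). At ρ = 0.3 and 0.7, SD_diff is 13.0 and 8.5. Repeating step 3 at shifts of 0, 2 and 4 mmHg gives paired power of 0.648, 0.640, 0.614 and of 0.947, 0.941, 0.920. The loss has a similar size throughout.

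**7. DSST and PVT.** Section 6 gives no effect size or SD for either, so no power figure can be given.

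**The case against.** The strongest reply is that the planned test is safe and the loss slight. With balanced sequences it is unbiased and its type I error does not exceed 0.050. A shift of half the target effect (2 mmHg) costs about one point of power, and a marked loss needs a shift larger than the 4 mmHg effect itself. The design also limits drift: a washout before each period, matched period lengths and documented changes in blood pressure medication.

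The bias case is also extreme. A 30:24 split puts all six leavers in one sequence, although both sequences receive sham. If each leaver were equally likely to come from either sequence, that has probability 2/64, or 3%. The expected imbalance is then 1.9 patients, which at a 2 mmHg shift gives a bias of 2 × 1.9/54 = 0.07 mmHg. Even at 30:24 the paired test's type I error stays just below 0.05 at a 2 mmHg shift. For shifts below about 1.5 mmHg its mean squared error is slightly lower than that of the adjusted estimate (variance 2.241 against 2.269).

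All of this stands, and it limits how much weight the point carries. It does not justify leaving the period out. The shift is unknown in advance, and the two possible errors are unequal: adjusting without need costs 0.02 points of power at 30:30, whereas failing to adjust costs about 4 points at a 4 mmHg shift. Section 10 (Study Design, item d) itself expects 10–15% dropout among patients who want therapy restored, so equal completion cannot be taken for granted.

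**Conclusion.** The concern holds. The treatment comparisons in Aims 1, 3, 5 and 6 ignore the randomised order. With balanced completion the consequence is lost efficiency, not bias: about 1 point of power at a 2 mmHg shift, 4 points at 4 mmHg and 7 points at 5.5 mmHg, with a conservative test. Bias needs both a period shift and unequal completion by sequence, and would usually be a fraction of a mmHg.

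These sizes rest on assumed shifts, 1:1 allocation and 11 mmHg as the SD of the difference. The cost of one degree of freedom is exact for balanced sequences. Under imbalance there is also a small loss of precision (SE 1.497 to 1.506 at 30:24). This is a worthwhile, nearly free improvement and not a threat to the trial's validity. A period term does not deal with carry-over, which is a separate matter.

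**What to change.** In Section 6, make the primary comparison in Aims 1, 3, 5 and 6 period-adjusted: the average of the two sequence-specific mean active-minus-sham differences, with SE = (pooled SD/2)·√(1/n₁ + 1/n₂) and n₁ + n₂ − 2 df. For patients with both measurements, a mixed model with treatment, period and sequence and a random patient effect is equivalent. It can also carry sex, which Section 6 names as a covariate in all analyses and a paired t-test cannot include. Report the difference with its 95% CI and the number of completers by sequence. Keep the paired t-test as a sensitivity analysis.

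The mixed model also keeps patients measured in only one period. That is a separate missing-data choice and should be stated as such. The gain is minor: power 0.746 to 0.751 at 10% dropout and 0.721 to 0.729 at 15%. This assumes a correlation of 0.5 and dropout during sham split evenly by sequence, so that only treatment-first leavers have a measured period.

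The cost is SAP wording and one degree of freedom, with no new data. If there is truly no period effect, power goes from 0.7912 to 0.7910 at 30:30 and from 0.747 to 0.741 at 30:24. The documents do not establish whether analysis has begun: the protocol is dated 09/30/2021, while Section 9 planned to complete recruitment in 2020. The change should be dated and made before the treatment comparison is run. If that has already happened, report the adjusted result beside the planned one and label it as added later.

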Aim 2a: Determine the impact of hypoglossal nerve stimulation on 24-hour diastolic ambulatory blood pressure in this cohort of patients with moderate-severe obstructive sleep apnea

Hypothesis: The mean 24-hour diastolic blood pressures will be improved at therapeutic levels of hypoglossal nerve stimulation and returned to pre-operative levels after 30-day sham period

Change in mean SLEEP systolic and diastolic ambulatory blood pressure values

Aim 2b: Determine the impact of hypoglossal nerve stimulation on mean sleep systolic and diastolic blood pressures in this cohort of patients with moderate-severe obstructive sleep apnea

Hypothesis: The mean sleep systolic and diastolic blood pressures will be improved at therapeutic levels of hypoglossal nerve stimulation and returned to pre-operative levels after 30-day sham period

Change in Pre-Ejection Period (PEP) duration

Aim 3: Determine the impact of hypoglossal nerve stimulation on pre-ejection period in this cohort of patients with moderate-severe obstructive sleep apnea

Hypothesis: The pre-ejection period will be improved at therapeutic levels of hypoglossal nerve stimulation and returned to pre-operative levels after 30-day sham period

Association of MSNA* and PEP with blood pressure measurements

Aim 4: Determine if MSNA and PEP are positively associated with blood pressure measurements after adjusting for confounders of age, sex, body-mass index, baseline systolic BP, baseline diastolic BP, antihypertensive medication use.

H1: There will be a significant association between alterations in systolic and diastolic blood pressure and muscle sympathetic nerve activity

H2: There will be a significant association between alterations in systolic and

diastolic blood pressure and pre-ejection period duration

*Note: MSNA was part of Emory University protocol and will not be performed at the University of Pennsylvania.

Change in Flow-mediated Dilation (FMD)

Aim 4a: Determine the impact of hypoglossal nerve stimulation on flow mediated dilation in this cohort of patients with moderate-severe obstructive sleep apnea

Hypothesis: The flow mediated dilation parameters will be improved at therapeutic levels of hypoglossal nerve stimulation and returned to pre-operative levels after 30-day sham period

Change in Pulse Wave Velocity (PWV)

Aim 4b: Determine the impact of hypoglossal nerve stimulation on pulse wave velocity in this cohort of patients with moderate-severe obstructive sleep apnea

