Risk/Benefit Ratio: As there are few risks in measuring cardiovascular data apart from recurrence of OSA symptoms during the 4-week sham period and there are the possible benefits of better understanding sleep apnea and how to treat people with sleep apnea in the future, the risks of participating in this study are outweighed by the potential benefits.

8. Device Management

Penn owns WatchPAT and ambulatory blood pressure devices, which will be managed, dispensed, and received back from subjects by the study team. Recordings will be handled and scored in accordance with best clinical practices.

9. Feasibility

Sample Size Feasibility: We have recruited 17 subjects (16 have successfully completed the study) since January, 2018, and plan to complete recruitment in 2020.

Technical Feasibility: With regard to Aim 1, 16 subjects successfully completed both sets of 24-hour ambulatory blood pressure testing.

Project execution feasibility: PI has 50% protected research time through 2021. PI will devote 20% of his efforts to ensure the successful completion of this project.

10. Potential Pitfalls, Solutions, and Contingency Plans

1. Study Design

a) The study sample reflects a selective subset of patients with moderate-severe OSA, limiting the generalizability of these findings. Among others, the inclusion criteria are 1) unable to consistently use PAP, and 2) body-mass index < 32 kg/m². In clinical practice, this represents only 20% of the moderate-severe OSA population as BMI > 32 kg/m² is an exclusion criterion for HGNS and roughly 50% of patients can comply with PAP. From a population health perspective, however, this selected group represents a not insignificant 2% of the U.S. adult population. ⁴ Note: since this research protocol was created, BMI was

removed as an exclusion criteria for HGNS.

- b) We are performing measurements at 2 time points only, immediately after sham and treatment interventions. While we do not capture baseline values, these measures will allow us to compare the individual effects of sham and active therapy. We predict that a 2-week washout period, in contrast to the 1-week withdrawal period in the STAR trial, ²³ will provide a return to baseline for ABP at 2 weeks. ³¹

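### Aim 4 hypothesises that alterations in blood pressure go with PEP, but its regression is written in levels and does not isolate the within-patient association

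*Combined protocol and SAP*

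**What the plan says.** Section 6 (Analysis, Aim 4) gives the model: "we will perform linear regression with MSNA bursts/min and PEP duration as outcome variable and systolic and diastolic blood pressures as main effect variables". The PEP hypothesis beneath it reads: "There will be a significant association between alterations in systolic and diastolic blood pressure and pre-ejection period duration". The word for change attaches at least to blood pressure; whether PEP is also meant as a change is left to the reader. The objectives in Section 3 put the aim in a third way, with no reference to change: "Determine if MSNA and PEP are positively associated with blood pressure measurements after adjusting for confounders".

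The Aim 4 covariate list is: "adjusting for confounders of age, sex, body-mass index, baseline systolic BP, baseline diastolic BP, antihypertensive medication use". It has no baseline PEP, no patient term and no sham/active term, and the text does not say whether the sham record, the active record or both enter the model. Section 10 (Study Design, item b) says: "We are performing measurements at 2 time points only, immediately after sham and treatment interventions". The next sentence there adds that baseline values are not collected.

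Power is stated thus: "With n=45, we would exceed 95% power to detect effects in the moderate to large range" (r² above 0.25), falling to 78% for r² above 0.16, two-tailed at 0.05.

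Elsewhere in Section 6 the authors do define change variables. The Aim 1 regression has blood pressure reduction as its outcome, and Aims 5 and 6 define improvement as the therapy score less the sham score.

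**The concern.** Each patient contributes two paired records, so the design can show whether patients whose pressure falls more on therapy are also those whose PEP moves more. That is what the hypotheses appear to ask. A regression of level on level need not show it. With one record per patient, the coefficient blends stable differences between people with the within-patient link. With both records stacked as independent rows, it blends the same two things and also treats correlated rows as independent.

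Two errors follow. A real link between the changes can be diluted and missed. A link that exists only between people can be reported as if changes in pressure and in sympathetic tone went together. The analyst would also have to choose among readings that can give opposite answers, after the data are in hand.

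**Working it through.** **1. The plan's own power.** Inputs from Section 6, Aim 4: n=45, two-sided 0.05, r=√0.16=0.40 and r=√0.25=0.50. For one correlation with one data point per patient, power = Φ(atanh(r)·√(n−3) − 1.960), with √42=6.481.
- r=0.40: 0.4236×6.481=2.746; 2.746−1.960=0.786; power 78.4% (stated 78%).
- r=0.50: 0.5493×6.481=3.560; 3.560−1.960=1.600; power 94.5% (stated above 95%; a noncentral t calculation gives 96.6%).

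The figures reproduce. They fit one-visit levels or change scores equally well, so they do not show which was meant.

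**2. What a level regression sees.** Let ρ be the within-patient correlation between visits (taken as equal for both measures), r_B the correlation of the stable patient components and r_W that of the visit-specific components. Then the one-visit correlation is ρ·r_B + (1−ρ)·r_W, and the correlation of changes is r_W. The documents give none of these, so the values below are assumptions. Tests are two-sided, so the sign does not matter.
- Changes linked only (r_B=0, r_W=−0.4, ρ=0.5): the level correlation is 0.5×(−0.4)=−0.20. Power: 0.2027×6.481=1.314; 1.314−1.960=−0.646; 26%. Change on change keeps r=−0.40, hence 78.4%.
- Patients linked only (r_B=−0.4, r_W=0, ρ=0.5): the level correlation is again −0.20, so about 26% of trials reject although the changes are unrelated.

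**3. Simulation.** 20,000 trials per scenario, n=45, ρ=0.5, without the age, sex, BMI and medication covariates. Share of trials with p<0.05:

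| Model | Changes linked (−0.4), patients not | Patients linked (−0.4), changes not |
|---|---|---|
| Change on change | 79% | 5% |
| One visit, levels | 27% | 26% |
| Both visits stacked | 49% | 48% |
| Active level adjusted for sham BP | 33% | 12% |

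At ρ=0.8 the first three rows become 79%, 8% and 19% in the first scenario, and 5%, 58% and 81% in the second. With both links null, stacking rejects in about 8% (ρ=0.5), 11% (ρ=0.7) and 13% (ρ=0.8) of trials.

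**4. The baseline covariate.** If a true baseline pressure existed, adjusting for it would move the pressure coefficient towards change given baseline. Section 10 rules that out, which leaves the sham value as the nearest candidate. The last row of the table shows the result: fewer false positives than the other level models, but not 5%, and power of only 33%.

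**5. Power of the change model with covariates.** With four covariates (age, sex, BMI, antihypertensive use), the Fisher formula for a partial correlation uses √(45−3−4)=√38=6.164.
- r=0.40: 0.4236×6.164−1.960=0.651, power about 74%.
- r=0.50: 0.5493×6.164−1.960=1.426, power about 92%.

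**6. A caution on mixed models.** A mixed model on within-patient pressure deviations without a sham/active term is change regression through the origin. Mean shifts in both measures then create an association by themselves. With Section 6's own targets (4 mmHg, SD 11; 10 ms, SD 17.3) and no individual link, it rejects in about 20% of trials at ρ=0.5 and 41% at ρ=0.7. Change regression with an intercept stays at 5%.

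**The case against.** The strongest reply is that this is loose wording rather than a wrong model. Section 6 opens by saying that the overall plan is to examine sham-to-treatment changes in the cardiovascular endpoints and their internal correlation. Read with the hypotheses, that makes change on change a plausible intention, and the power statement is compatible with it. This stands: a reader might infer that the plan definitely tests differences between patients, but that is certain only if one visit per patient is used, and the plan does not say so. The opening statement does not define a model, however, and the Aim 4 sentence departs from it.

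Section 3 speaks only of blood pressure measurements, and under that wording an association between patients would be a legitimate answer. That too stands; the conflict is with the hypotheses.

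The plan also adjusts for age, sex, BMI and medication, which would remove some confounding between patients. The simulated rates should therefore not be read as the error rates of the planned adjusted model. The covariates remove only what they measure, and they do not restore the diluted within-patient signal.

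Finally, a reader might infer that Aim 4 is meant to estimate the effect of therapy on PEP. It is not: the Aim 3 paired t-test does that. Even change on change asks only whether the two changes go together.

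**Conclusion.** The point holds as a mismatch between hypothesis and model. The hypotheses concern alterations; the model is in levels, names no visit, change score or patient term, and includes a baseline covariate that the design does not supply. None of the level readings tried serves the stated hypothesis well. At an assumed within-patient correlation of 0.5 and a change correlation of −0.4, power is 27 to 49% against about 79%. With a between-patient link only, rejection is 12 to 48% against 5%. The sizes depend on correlations that the documents do not give and on omitting the four patient covariates, so they illustrate direction and order of magnitude only.

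The stated power is not in error; it applies to the hypothesis only if r is the correlation of changes. The consequences are limited: Aim 4 is secondary, its MSNA part is not performed at this site, and the primary 24-hour systolic comparison is untouched. The plan should still be changed, because the better analysis uses the same data.

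**What to change.** In Section 6, Aim 4, specify one row per patient: regress PEP (active minus sham) on 24-hour systolic pressure (active minus sham), with an intercept, adjusting for age, sex, BMI and antihypertensive use. Fit a separate model for diastolic pressure. Drop the baseline pressure covariates, or define them from a value that the study records. Align the Section 3 wording with the hypotheses, and state that the r² in the power statement refers to changes.

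If a mixed model is preferred, split pressure into the patient mean and the within-patient deviation, test the deviation, and include a treatment (sham/active) term.

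The cost is SAP wording only, with no new visits or data. The small downside is that change scores carry measurement error from two visits.
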